9.4 Vital Signs, Physical Findings, and Other Observations Related to Safety

9.4.1 Vital Signs

Baseline will be defined as the last vital sign value obtained before the first dose of study drug on Day 1; if Day 1 values are unavailable, then values obtained at the Screening Visit will be used. Observed vital sign measurements along with change from baseline for each scheduled assessment will be summarized descriptively by treatment group and visit for each vital sign variable specified in the protocol (Systolic Blood Pressure, Diastolic Blood Pressure, Pulse Rate, Respiratory Rate, and Oral Temperature). Vital signs will also be presented for each patient in a data listing.

9.4.2 ECG

Observed Overall ECG Interpretations will be summarized as Normal, Abnormal and Not Clinically Significant, or Abnormal and Clinically Significant for each scheduled visit by treatment group. In addition, observed and change from baseline measurements of ECG intervals (PR, QT, QTcF, QRS, and RR) for each scheduled assessment will be summarized descriptively by treatment group and visit as well as listed within a by-patient data listing. Patients receiving study drug will be identified and summarized by treatment group and visit, as well as overall for the following clinically notable categories:

- QTcF > baseline and > 450 msec
- QTcF > baseline and > 480 msec
- QTcF > baseline and > 500 msec
- QTcF increase from baseline > 30 msec
- QTcF increase from baseline > 60 msec

9.4.3 Physical Examinations

A listing of physical examinations will be provided. Deteriorations from baseline on physical examination will be coded as adverse events and summarized as such.

10. PHARMACOKINETIC EVALUATION

10.1 Pharmacokinetic and Pharmacodynamic Methods

The collection status of pharmacokinetic and pharmacodynamic samples will be listed for each visit with scheduled sampling by patient using the Safety Population. Plasma concentrations of study drug may be summarized separately, as appropriate, for the Pharmacokinetic Population.

11. INTERIM ANALYSES AND DATA MONITORING

When SALT data through Week 24 of treatment was available for all patients in Cohort 1 (4 mg) and Cohort 2 (8 mg), an interim analysis was performed. The purpose was to review selected efficacy and safety results in those 2 cohorts for planning purposes regarding the clinical development of the compound. While the results showed aggregate comparisons between the patients who received active CTP-543 and those who received placebo, all blinded study personnel remained blinded to treatment assignment. Since no further enrollment occurred in these 2 cohorts, there will be no adjustment for multiple treatment group comparisons. See Section 14 and 15 for summary tables and figures that were generated for this interim analysis.

A Data Monitoring Committee will monitor safety at regular intervals as defined in the DMC Charter. After the last patient in a cohort has completed the Week 12 Visit, the DMC will convene to review accumulated safety data to assess if initiation of the subsequent cohort is supported, as applicable. Specifications of data to be supplied to the Committee are outside the scope of this document. Further details are provided in the latest version of the DMC Charter.

12. CHANGES TO THE ANALYSES PLANNED IN THE PROTOCOL

The following alterations were made to the original analyses planned in the protocol:

- SALT 50% reduction analysis changed from Cochran-Mantel-Haenszel Test (CMH) to χ^2 test and will not be stratified by Alopecia Areata subtype.
- VAS-S analysis method changed from CMH to ANCOVA.
- CGI-I and PGI-I analysis method changed from CMH test to χ^2 test.
- AASIS and Exploratory Question analysis method changed from ANCOVA to descriptive statistics and χ^2 test, respectively.
- Alopecia Areata subtype used as a fixed effect within the MMRM.
- TEAE definition modified so that all AEs that occur after study dosing will be counted, rather than only those that occur up to Week 24 or the Early Termination Visit.

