#### **Exploratory Efficacy Endpoints**

Treatment differences for relative change in SALT score from baseline to Weeks 4, 8, 12, 16, 20, and 24 will be assessed with a mixed-effect model of repeated measures (MMRM) model. The model will include fixed factors for treatment group, study visit, and treatment by study visit interaction, with baseline SALT score as a covariate. An unstructured variance-covariance matrix will be used.

Treatment differences for the Global Impression of Improvement and VAS scales will be assessed with the Cochran-Mantel-Haenszel test using the alopecia areata subtype as the stratification factor.

Change in symptoms as measured by AASIS and the exploratory questions from baseline to Week 24 will be assessed with the analysis of covariance with a fixed factor for treatment and baseline value as a covariate.

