3. GENERAL ANALYSIS AND REPORTING CONVENTIONS

The following is a list of general analysis and reporting conventions to be applied to this study, unless otherwise specified.

All data displays (tables, listings, and figures) will have a header showing the sponsor company name, protocol number, page number, and display status (i.e. “DRAFT” or “FINAL”), as well as a footer indicating path, file name, and run date/time. Summary tables and data listings will be summarized by treatment and overall, as appropriate. All data collected per-protocol and all derived variables will be listed.

Categorical variables will be summarized using counts (n) and percentages (%) and will be presented in the form “n (xx.x).” If a count is 0, 0% will be shown for the percentage. If a percentage is 100%, 100% will be shown with no decimal place. To ensure completeness, summaries for categorical variables will include all categories, even if no patients had a response in a particular category. Unless otherwise specified, the denominator for each percentage will be based on the number of patients in the population being summarized (header n). If missing values are present, counts will be shown but will not be included in percentage calculations.

Continuous variables will be summarized using mean, standard deviation (SD), minimum, maximum, median, and number of patients. The mean and median will be reported to an additional level of precision than the original observations, and the SD will be reported to two additional levels of precision than the original observations. The minimum and maximum will be the same precision as the original data. In general, any calculated values, such as those due to unit conversion, will be rounded to the same number of decimal places as the original data.

All statistical tests will be 2-sided with a significance value of 0.05. Testing will be performed only for the Treatment Period. Estimates and confidence intervals will be reported to 1 more decimal than the original data. P-values will be reported to 3 decimal places.

Summary tables and data listings:

- No preliminary rounding will be performed; rounding will only occur after analysis.
- Data from patients excluded from an analysis population will be presented in the data listings but will not be included in the calculation of summary statistics, where applicable.

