8.4 Analysis Methods

All statistical tests will be 2-sided with a significance value of 0.05. Testing will be based on the Efficacy population and performed only for the Treatment Period. An analysis of the primary efficacy endpoint and exploratory SALT endpoints will also be performed for the Per Protocol population. The final efficacy analysis will be conducted when all patients in the 12 mg cohort have completed Week 24. The placebo groups from all 3 cohorts will be pooled and compared to each active dose (4 mg, 8 mg, and 12 mg) individually. Active doses, 4 mg, 8 mg, and 12 mg, will also be compared. There will be no adjustment for multiple treatment group comparisons in this dose-ranging Phase 2 study.

Table 8-1 gives an overview of the analysis methods that will be used for each of the efficacy variables.

Table 8-1 Efficacy Variables and Analysis Methods

Efficacy Variables	Collection Times	Method
Primary		
Responder Analysis SALT (50% relative reduction)	Baseline, Week 24	χ^2 Test
Exploratory		
Responder Analysis SALT (50% relative reduction)	Baseline, Week 4, 8, 12, 16, 20	χ^2 Test
Responder Analysis SALT (75%, 90%, and 100% relative reduction)	Baseline, Week 4, 8, 12, 16, 20, 24	χ^2 Test
SALT (≤ 10 , ≤ 20 , ≤ 25 absolute score)	Baseline, Week 4, 8, 12, 16, 20, 24	χ^2 Test
SALT (absolute change)	Baseline, Week 4, 8, 12, 16, 20, 24	MMRM
SALT (relative change)	Baseline, Week 4, 8, 12, 16, 20, 24	MMRM
SALT (absolute score)	Baseline, Week 4, 8, 12, 16, 20, 24	MMRM
Clinician VAS-S (percent change)	Baseline, Week 12, 24	ANCOVA
Patient VAS-S (percent change)	Baseline, Week 12, 24	ANCOVA
CGI-I	Week 12, 24	χ^2 Test
CGI-I Responder (“Very Much/Much Improved” and “Much/Very Much Worse”)	Week 12, 24	χ^2 Test
PGI-I	Week 12, 24	χ^2 Test
PGI-I Responder (“Very Much/Much Improved” and “Much/Very Much Worse”)	Week 12, 24	χ^2 Test
AASIS	Baseline, Week 24	Descriptive Statistics
Exploratory Questions	Baseline, Week 24	Descriptive Statistics
Responder Analysis, Exploratory Questions, Satisfied v. Unsatisfied	Baseline, Week 24	χ^2 Test

χ^2 = Chi-Squared Test; ANCOVA = analysis of covariance; CMH = Cochran-Mantel-Haenszel; MMRM = mixed-effect model for repeated measures

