A χ^2 trend test will be used to analyze CGI-I and PGI-I between treatment groups overall. Responses for PGI-I and CGI-I categorized as achieving “Very Much/Much Improved” or “Much/Very Much Worse” will also be compared between treatment groups with the χ^2 test. Descriptive statistics and by-patient data listings will also be presented for the 7 response categories for each assessment.

Mean and mean change from baseline for total AASIS score will be reported. Number and percentage of subjects in each response category of AASIS will also be summarized. Individual responses will be listed in categories of “Severity” and “Interference”.

The exploratory questions will be summarized with descriptive statistics at baseline and Week 24, and will be listed in the by-patient data listings. Responses will be categorized as “Satisfied” (including responses of “Very satisfied” and “Satisfied”) and “Unsatisfied” (including responses of “Unsatisfied” and “Very unsatisfied”) and presented as a 2 x 2 shift table from baseline to Week 24, compared with a χ^2 Test by cohort.

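### The SAP replaces the protocol's baseline-adjusted AASIS analysis with descriptive statistics, leaving the AASIS objective with no planned between-group estimate or confidence interval

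*SAP*

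**What the plan says.** Protocol 12.4.2 (Exploratory Efficacy Endpoints) states that AASIS change from baseline to Week 24 "will be assessed with the analysis of covariance with a fixed factor for treatment and baseline value as a covariate".

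The SAP withdraws this in three places:

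- Section 12: "AASIS and Exploratory Question analysis method changed from ANCOVA to descriptive statistics"; the same entry goes on to name a chi-squared test for the exploratory questions. AASIS therefore becomes descriptive, while the exploratory questions keep a test.
- Table 8-1 gives the AASIS method as "Descriptive Statistics".
- Section 8.4.2: "Mean and mean change from baseline for total AASIS score will be reported", and "Number and percentage of subjects in each response category of AASIS will also be summarized".

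Section 3 defines a continuous summary: "Continuous variables will be summarized using mean, standard deviation (SD), minimum, maximum, median, and number of patients". That contains no group difference and no interval. The two AASIS tables listed in SAP section 14 (14.2.5.1 and 14.2.5.2) are a response summary and a table of means and mean changes. Neither title indicates a comparison.

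Change in AASIS is still an exploratory objective (SAP 2.1.2) and an exploratory endpoint (SAP 8.2). The schedule of events collects AASIS on Day 1 and at Week 24. For clinician and patient VAS-S, SAP 8.4.2 plans an ANCOVA with treatment, subtype and baseline, giving least squares means with 95% CIs and a p-value for each treatment comparison.

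**The concern.** The SAP keeps the AASIS objective but removes the only analysis that would estimate a treatment difference for it. The same list of changes moves VAS-S to ANCOVA, so the single-line patient scale gets a baseline-adjusted analysis and the 13-item patient questionnaire gets none. No reason is recorded for treating them differently.

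Readers of the report will compare the tabulated mean changes across groups anyway. That informal comparison is unadjusted for baseline. It is also less precise than ANCOVA if baseline and Week 24 scores are positively but imperfectly correlated with equal variances. Baseline imbalance is a live possibility because the cohorts are sequential and placebo is pooled over all three. What is at stake is the usefulness of one exploratory patient-reported outcome, not the primary result.

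**Working it through.** **1. The plan's own figures.** The documents give no AASIS standard deviation, effect size or correlation, so there is no AASIS figure to reproduce. The one power statement (SAP 2.6: 28 v 28, 45% v 10%, two-sided 0.05, more than 80%) concerns SALT responders. With pooled null variance:

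(0.35 × √28 − 1.96 × √(2 × 0.275 × 0.725)) / √(0.45 × 0.55 + 0.10 × 0.90) = (1.852 − 1.238) / 0.581 = 1.06, which is 85.5% power.

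The statement holds but does not bear on AASIS. Only the group size of 28 is used below.

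**2. Is the VAS-S type of model applicable?** Protocol Appendix 17.3.1 has 7 severity and 6 interference items, each scored 0 to 10. SAP 8.2.4 sums all responses, so the total runs from 0 to 13 × 10 = 130. It is a numeric score with a Day 1 value, and an ANCOVA of change can be fitted.

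**3. Precision.** Assume the same standard deviation σ at both times, correlation r, and n per group.

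- Unadjusted difference in mean change: variance = 2σ²(1 − r) × 2/n
- ANCOVA difference: variance = σ²(1 − r²) × 2/n
- Ratio: (1 − r²) / (2(1 − r)) = (1 + r)/2

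With n = 28, the 95% half-width is 1.96 × √(2/28) = 0.524, multiplied by √(1 − r²) for ANCOVA or by √(2(1 − r)) for change:

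| assumed r | variance ratio | SE ratio | ANCOVA half-width (SD) | change half-width (SD) |
|---|---|---|---|---|
| 0.3 | 0.65 | 0.81 | 0.50 | 0.62 |
| 0.5 | 0.75 | 0.87 | 0.45 | 0.52 |
| 0.7 | 0.85 | 0.92 | 0.37 | 0.41 |

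ANCOVA would have 15% to 35% less variance over this range. One degree of freedom for baseline is ignored.

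**4. Baseline imbalance.** Under the same assumptions the regression slope on baseline is r, whereas a change score uses a slope of 1. If two groups differ by d at baseline, the two estimates differ by (1 − r)d, which is 0.7d at r = 0.3 and 0.3d at r = 0.7.

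**5. How much placebo is concurrent.** The ratios are 2:1, 2:1 and 5:1. If each active group has N patients (assumed), pooled placebo is N/2 + N/2 + N/5 = 1.2N. Only 0.2/1.2, about 17%, was randomised alongside the 12 mg group. Randomisation alone therefore does not balance baseline AASIS between 12 mg and most of its comparator.

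**The case against.** The strongest case against is that this is a declared, low-ranking choice. The protocol defers statistical detail to the SAP, the SAP undertakes to document changes before database lock, and section 12 lists this one. None of the six changes listed there carries a reason, so the silence does not single out AASIS. The study is a dose-ranging Phase 2 trial with many unadjusted exploratory tests already. Read literally, the objective of assessing change in AASIS is met by a mean change. All of this lowers the weight. It does not supply a treatment estimate, and an estimate with an interval need not be read as another test.

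Second, the planned output is more than group means. Item category counts and listings are planned, and if the section 3 convention is applied to change, its SD and n would let a reader work out an unadjusted difference and interval. That stands. What is missing is the adjustment and any planned presentation of a difference. The table shells (Attachment A) are not available to check.

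Third, the precision gain is measured against a comparison the SAP does not plan, and it rests on assumed correlations. That also stands: the 0.65 to 0.85 describes the reader's informal comparison, not a loss within a planned analysis.

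Fourth, adjusting for baseline AASIS does not cure pooling over sequential cohorts. It deals with measured imbalance in that score and nothing else.

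Fifth, the model raises a missing-data question. About 20% non-completion is planned for (150 to 120), LOCF in SAP 8.3.1 covers SALT only, and the Week 24 visit doubles as the Early Termination Visit. This is a real cost, although the descriptive Week 24 tables need the same rule.

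**Conclusion.** The point holds and is minor. The SAP gives the AASIS objective no planned between-group estimate or confidence interval, and states no reason for dropping the protocol's ANCOVA. If an unadjusted comparison of mean changes is the alternative, ANCOVA would have 0.65 to 0.85 of its variance. That range assumes correlations of 0.3 to 0.7 and equal variances; the documents support neither figure, and that baseline predicts Week 24 is itself an assumption. The primary conclusion is unaffected.

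A reader might go further in four ways that the documents do not support:

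- That this is a hidden departure, or one driven by the interim results. It is openly listed in section 12, and no AASIS table in section 14 is marked for the interim analysis.
- That the exploratory questions also lost their test. They keep a chi-squared test.
- That only group means remain. Item category counts and listings are planned too.
- That restoring ANCOVA would make the pooled placebo comparison safe. Other differences between sequential cohorts would remain.

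**What to change.** Reinstate an exploratory ANCOVA of change in AASIS total at Week 24, with treatment and baseline AASIS as in the protocol. Add alopecia subtype and declare it in section 12 as a modification: the protocol model has no subtype term, but the SAP's VAS-S model does. Report the LS-mean difference and 95% CI for each dose against pooled placebo, labelled exploratory. The difference and its interval should be named explicitly, since the VAS-S text promises intervals for least squares means without clearly promising one for the difference. State how missing Week 24 scores and scores from early-termination visits are handled. Keep the descriptive tables.

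The edits fall in SAP 8.3.1, 8.4.2, Table 8-1, section 12 and one added table in section 14. No new data are needed. The cost is one extra exploratory model, a missing-data rule, and one more set of comparisons without multiplicity adjustment. If the sponsor prefers to stay descriptive, section 12 should at least say why.

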## **11. ADVERSE EVENTS**

### **11.1.1. Definition of Adverse Event**

An adverse event is any untoward medical occurrence that may appear or worsen in a patient during the course of a study. It may be a new intercurrent illness, a worsening concomitant illness, an injury, or any concomitant impairment of the patient's health, including laboratory test values, regardless of etiology. Any worsening (ie, any clinically significant adverse change in the frequency or intensity of a pre-existing condition) should be considered an adverse event. A diagnosis or syndrome should be recorded on the adverse event page of the eCRF rather than the individual signs or symptoms of the diagnosis or syndrome. A worsening of the condition under study, alopecia areata, will not be reported as an adverse event.

All patients will be monitored for adverse events during the study. Assessments may include monitoring of the following parameters: the patient's clinical symptoms, laboratory, physical examination findings, or findings from other tests and/or procedures.

An adverse event reported after informed consent, but before the first dose of study drug (ie, Day 1), will be considered a pretreatment adverse event and will be captured on the eCRF. Adverse events will be considered treatment-emergent if the onset is after the first dose of study drug.

An abnormal laboratory value is considered to be an adverse event if the abnormality:

- results in discontinuation from the study;
- is judged by the Investigator to be of significant clinical importance requiring treatment, modification/interruption of investigational product dose, or any other therapeutic intervention

Regardless of severity grade, only laboratory abnormalities that fulfill a seriousness criterion need to be documented as a serious adverse event.

If a laboratory abnormality is one component of a diagnosis or syndrome, then only the diagnosis or syndrome should be recorded on the adverse event eCRF. If the abnormality was not a part of a diagnosis or syndrome, then the laboratory abnormality should be recorded as the adverse event. If possible, the laboratory abnormality should be recorded as a medical term and not simply as an abnormal laboratory result (e.g., record thrombocytopenia rather than decreased platelets).

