#### **11.1.6. Reporting Adverse Events**

The Investigator must report to Sponsor or its designee all adverse events that occur during the study from the time written informed consent is given until the final study visit or early termination, regardless of their relationship to the study drug. Serious adverse events and pregnancies will be reported from the time written informed consent is given through 30 days beyond the last dose of study drug.

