#### **Adverse Events**

An adverse event reported after informed consent, but before the first dose of study drug (i.e., Day 1), will be considered a pre-treatment adverse event. Treatment-emergent adverse events (TEAEs) will be defined as any adverse event that occurs after administration of the first dose of study drug until Week 24 or the Early Termination Visit. The number and percentage of patients who report TEAEs will be summarized by system organ class and preferred term.

Treatment emergent adverse events will also be summarized by intensity as well as relationship to study drug.

Patients who report the same preferred term on multiple occasions will be counted once for the preferred term: under the highest severity when summarized by severity and under the closest relationship to study drug when summarized by relationship. If a patient reports multiple preferred terms for a system organ class, the patient will be counted only once for that system organ class.

Proportions for adverse events that are gender-specific (e.g., dysmenorrhea) will be based on the number of patients from that gender.

The number and percentage of patients who experience TEAEs will be summarized by treatment group for the following:

- By system organ class and preferred term
- By severity/intensity, system organ class, and preferred term
- By relationship to study drug, system organ class, and preferred term
- Serious adverse events by system organ class and preferred term

- Serious adverse events by relationship to study drug, system organ class, and preferred term
- Adverse events resulting in discontinuation of study drug by system organ class and preferred term
- Adverse events that result in study drug dose interruption by system organ class and preferred term

By-patient listings will be provided for any deaths, serious adverse events, and adverse events leading to discontinuation of treatment. Treatment-emergent adverse events that result in dose interruption will also be identified.

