Patients will provide appropriately obtained informed consent prior to completing any screening procedures. Patients meeting screening criteria will be eligible to continue to the Day 1 visit for review of eligibility and baseline assessments, including SALT, physical examination, clinical laboratory assessments, vital signs, and electrocardiogram (ECG). For each cohort, patients meeting all inclusion criteria and none of the exclusion criteria will be randomized to CTP-543 treatment or placebo. The first 2 cohorts will be randomized in a 2:1 ratio (active:placebo) and the third cohort will be randomized in a 5:1 ratio (active:placebo) in order to provide a similar number of patients across each CTP-543 dose and overall placebo (pooled) group. Randomization will be stratified by classification of alopecia areata subtype into one of the following three categories: 1) alopecia areata, 2) alopecia totalis or alopecia universalis, or 3) alopecia ophiasis.

The double-blind, placebo-controlled Treatment Period for each cohort will last 24 weeks. Assessment of treatment response with SALT for efficacy will occur at 4, 8, 12, 16, 20 and 24 weeks. The final efficacy analysis will be conducted when all patients in the 12 mg cohort have completed Week 24.

For Cohorts 1 and 2, patients will stop taking study medication upon completion of treatment at Week 24 and enter a 4-week Post-Treatment Safety Follow-Up Period. Patients will be assessed for safety through Week 28. For Cohort 3, patients will either complete treatment at Week 24 and have a Safety Follow-up visit at Week 28 prior to exiting the study, or if eligible, may enroll into an Open-label Extension study of CTP-543 at their Week 24 visit.

Patients enrolled into each cohort will take the first dose of study drug in the clinic on Day 1 and will be instructed to take study drug every 12 hours for the duration of the Treatment Period. Patients will dose study drug in the clinic on all Study Visit Days after clinical laboratory blood draws are completed. Blood samples for pharmacokinetic and pharmacodynamic assessment will be taken periodically. Scheduled assessment of patient and clinician perception of disease

severity and improvement will also occur. Patient safety will be monitored throughout the trial and supported by regular review by the DMC.

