9.2 Adverse Events

Adverse events will be coded using MedDRA and summarized by system organ class and preferred term. Clinically significant deteriorations in physical examination findings will be reported and summarized as adverse events.

An adverse event reported after informed consent, but before the first dose of study drug (i.e., Day 1), will be considered a pre-treatment adverse event. Treatment-emergent adverse events will be defined as any adverse event that occurs after administration of the first dose of study drug. The number and percentage of patients who report TEAEs will be summarized by system organ class and preferred term.

Treatment emergent adverse events will also be summarized by intensity as well as relationship to study drug.

Partial dates will be imputed for the purposes of defining TEAEs as follows:

- For a missing start day where the month and year are present, the start day will be set to the first day of the month, unless 1) the first day of the month is before the date of

administration of study drug and the month and year are the same as the month and year of the date of administration of study drug, and 2) the end date is on or after the date of administration of study drug or the end date is completely missing, in which case the start day will be set to the first day of administration of study drug.

- For a missing start day and month where the year is present, the start day and month will be set to January 1st, unless 1) January 1st is before the date of administration of study drug, and 2) the end date is on or after the date of administration of study drug or the end date is completely missing, in which case the start day and month will be set to that of the first date of administration of study drug.
- For a missing end day where the month and year are present, the end day will be set to the last day of the month, unless the month and year are the same as the month and year of the last contact date for the patient, in which case the end day will be set to that of the patient's last contact date.
- For a missing end day and month where the year is present, the end day and month will be set to the patient's last contact date, unless the year of the patient's last contact date is greater than the end year, in which case the end day and month will be set to December 31st.

For an entirely missing stop date (i.e. day, month, and year are missing), the TEAE will be treated as ongoing.

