
AASIS = Alopecia Areata Symptom Impact Scale; HBV= hepatitis B virus; HCV = hepatitis C virus
 
¹ All subsequent visits and week increments should be based on the date of Visit 2. All visit windows are ± 3 days.
 
² Serum pregnancy test only for females of childbearing potential.
 
³ Includes hematology and serum chemistry.
 
⁴ Will include thyroid stimulating hormone and hemoglobin A1c at Screening only.
 
⁵ Includes total cholesterol, low-density lipoprotein, high-density lipoprotein, and triglycerides.
 
⁶ Collected at Day 1 and Week 4 (pre-dose, and post-dose at end of visit), and Weeks 2 (pre-dose with clinical labs), and Weeks 8, 24 (post-dose at end of visit).
	
⁷ Collected at Day 1 and Week 2 (pre-dose with clinical labs), and Weeks 4, 8, 24 (post-dose at end of visit).⁸ Collected pre-dose.
 
⁹ Should be performed by the same rater for the patient for the duration of the study.
 
¹⁰ Collection is ongoing.
 
¹¹ Also serves as the Early Termination Visit for patient withdrawal.
 
¹² Randomization/Day 1 may occur any time after Screening laboratory results are available and reviewed by the Investigator.
 
¹³ The Safety Follow-Up Visit is intended for those patients in Cohort 1 and Cohort 2, and those patients in Cohort 3 who do not roll over into the Open-label Extension.

---	--

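### With no end date on TEAEs, Cohort 1–2 completers count to Week 28 but Cohort 3 rollovers only to Week 24, which can slightly lower non-serious TEAE percentages at 12 mg

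*SAP*

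**What the plan says.** **Definition.** SAP section 9.2 defines a treatment-emergent adverse event (TEAE) as "any adverse event that occurs after administration of the first dose of study drug", with no end. SAP section 12 lists this as a deliberate change: "all AEs that occur after study dosing will be counted, rather than only those that occur up to Week 24". The protocol has two versions. Section 12.4.6 closes the window: "any adverse event that occurs after administration of the first dose of study drug until Week 24 or the Early Termination Visit". Section 11.1.1 leaves it open: "Adverse events will be considered treatment-emergent if the onset is after the first dose of study drug".

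**Collection.** Protocol section 11.1.6 has the investigator report "all adverse events that occur during the study from the time written informed consent is given until the final study visit or early termination". Serious events follow a different rule and run "through 30 days beyond the last dose of study drug".

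**Final visit.** Cohort 1 and 2 completers stop drug at Week 24 and are followed off drug to Week 28. Under SAP section 2.2, eligible Cohort 3 patients "may enroll into an Open-label Extension study of CTP-543 at their Week 24 visit". Footnote 13 of the schedule in SAP section 17.2 reserves the Week 28 visit for Cohorts 1 and 2 and "those patients in Cohort 3 who do not roll over into the Open-label Extension".

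**Tables.** TEAEs are shown as numbers and percentages by treatment group (SAP section 9.2), with placebo pooled over the three cohorts (SAP section 3). Section 9.2 also plans incidence and prevalence tables for Weeks 0–12 and 12–24, repeated for Grade 3–4 hematology and chemistry events. Safety summaries are descriptive (SAP section 9.1).

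**The concern.** The definition has no end date, so the period that counts is set by how long events are collected, and that depends on cohort. A Cohort 1 or 2 completer contributes up to 28 weeks and a Cohort 3 rollover 24. Only Cohort 3 has the extension option, so the shorter period falls on the 12 mg arm and on the small share of placebo randomized alongside it.

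A shorter period can only remove events. If risk and dropout were the same in every group, non-serious TEAE percentages could come out lower at 12 mg than in the comparison groups, but not higher. Safety is a primary objective, and these tables are where a reader will compare doses. SAP section 12 declares the new definition but does not discuss how it interacts with the extension, and no exposure-adjusted rate or Week 24–28 table is planned.

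**Working it through.** **1. Length of the window.** The protocol synopsis gives 4 weeks of screening + 24 of treatment + 4 of follow-up = 32 weeks, its own figure. Without screening, 28 weeks remain after first dose. A rollover has 24, which is 4 weeks or 4/28 = 14.3% less. Those 4 weeks are off drug; for completers, events up to Week 24 are counted alike in all groups.

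**2. Inputs from the documents.**
- Completion: 120/150 = 80% (SAP section 2.6).
- Allocation: 2:1, 2:1 and 5:1. With equal active arms of size a, placebo is a/2 + a/2 + a/5 = 1.2a. Then 4.2a = 150, so a = 35.7.
- Cohort 1–2 share of pooled placebo: a/1.2a = 83.3%. With three equal cohorts of 50 it is 33.3/41.7 = 80%.

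**3. Assumptions, none given in the documents.** p is the 24-week incidence, r the share of Cohort 3 completers who roll over, and f the off-drug hazard as a fraction of the on-drug hazard. Early terminators are assumed to be equally ascertained in all groups.

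**4. Formula.** With constant hazards and a share c followed to Week 28:

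incidence = p + c(1 − p)[1 − (1 − p)^(f × 4/24)]

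Here c = 0.8 in Cohorts 1–2 and 0.8(1 − r) in Cohort 3. The gap between 4 or 8 mg and 12 mg is

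gap = 0.8 r (1 − p)[1 − (1 − p)^(f/6)]

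Example with p = 0.60, r = 1, f = 1: 0.8 × 0.4 × (1 − 0.4^(1/6)) = 0.32 × 0.1416 = 0.0453, that is 64.5% against 60.0%.

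**5. Results.** The standard error of a difference is √(2p(1 − p)/35.7).

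| 24-week incidence | Gap, r = 1, f = 1 (points) | Patients of 35.7 | Gap, r = 0.6, f = 0.5 (points) | SE (points) |
|---|---|---|---|---|
| 5% | 0.65 | 0.23 | 0.19 | 5.2 |
| 10% | 1.25 | 0.45 | 0.38 | 7.1 |
| 30% | 3.23 | 1.15 | 0.98 | 10.8 |
| 60% | 4.53 | 1.62 | 1.41 | 11.6 |
| 80% | 3.76 | 1.34 | 1.20 | 9.5 |

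With r = 1 and f = 1 the gap is 0.8(q − q^(7/6)), where q = 1 − p. It is largest at q = (6/7)^6 = 0.397, or p = 60.3%, so 4.5 points is the ceiling at 80% completion. With no dropout the ceiling would be 4.53/0.8 = 5.7. The gap is 0 if nobody rolls over or nothing happens off drug.

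**6. Against pooled placebo.** Cohort 3 placebo patients can also roll over, so the gap is 0.80 to 0.833 times the values above: at most 3.6 to 3.8 points at 60% incidence, and 1.0 at 10%.

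**7. Which tables lack an equal-window version.** The interval tables stop at Week 24, so they are unaffected for all TEAEs by system organ class and preferred term and for Grade 3–4 laboratory events. They do not give a cumulative 24-week count. The severity and relationship tables (14.3.1.8, 14.3.1.15) have no interval version.

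**8. Laboratory summaries, a separate matter.** SAP section 9.3 also gives Grade 3–4 results over all post-baseline visits combined. Week 28 adds one assessment that rollovers lack: hematology 9 instead of 8 (Weeks 2, 4, 6, 8, 12, 16, 20, 24), lipids 3 instead of 2 (Weeks 12, 24).

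**The case against.** The case for leaving the plan alone is strong. The change is disclosed. The protocol contradicts itself, and the SAP settles the conflict towards counting more safety events. The window has a practical end, because collection stops. What 12 mg rollovers lack is off-drug follow-up, not on-treatment events. Even the ceiling is under two patients per arm, and it needs full rollover, incidence near 60% and an off-drug hazard as high as on drug, all at once. All of this stands and keeps the point minor. What remains is that the main cumulative, severity and relationship tables have no version with equal follow-up.

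Stronger inferences are tempting, but the documents do not support them:

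- *That the plan materially understates 12 mg toxicity.* The inputs needed to say so are absent, and the modelled gap is below sampling error throughout.
- *That serious events are undercounted in the same way.* They are reported to 30 days after last dose, and the SAP does not say how those arising after rollover are assigned. The direction is unsettled, so there is no case for truncating the SAE tables.
- *That the protocol's Week 24 bound should also govern laboratory and ECG summaries.* It applies to TEAEs only. The protocol's laboratory and ECG sections have no such limit.
- *That restoring the protocol's cut-off is cost-free.* It would also end counting at the Early Termination Visit, although protocol section 8.3.1 has withdrawn patients return for safety follow-up. If withdrawal were more frequent at 12 mg, that cut could itself lower 12 mg.

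Two things remain open. The extension protocol was not supplied, so it is inferred from the collection rule that later non-serious events are recorded there. An off-drug hazard above the on-drug hazard was not modelled and would widen the gap; protocol section 4.4.1 lists symptom exacerbation after stopping among ruxolitinib's label warnings, without a rate.

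**Conclusion.** The point holds as a minor one. For non-serious events, the SAP's open window compares up to 28 weeks in Cohort 1–2 completers, and so in most of pooled placebo, with 24 weeks in 12 mg rollovers. At equal risk and equal dropout the artefact can only lower 12 mg. Its size is unknown. Under constant hazards and 80% completion it lies between 0 and about 4.5 points against 4 or 8 mg, and at about 0.4 points (10% incidence) to 1.4 points (60% incidence) with 60% rollover and half the on-drug hazard.

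No hypothesis test depends on it, nor does any escalation decision. The comparison of 12 mg with its own cohort's placebo is balanced by design, but that group is only about 35.7/5 = 7 to 50/6 = 8 patients and is shown separately only in listings. The reason to act is that the artefact is tied to dose, sits in a primary safety comparison and is cheap to remove.

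**What to change.** Keep the SAP's all-events definition for the listings, the SAE tables and the full TEAE tables. Then:

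1. For Tables 14.3.1.1, 14.3.1.2, 14.3.1.8 and 14.3.1.15, add a version limited to onset from first dose to Week 24 in every group, and name it as the basis for comparing doses. Apply the same Week 24 limit to patients who withdraw, rather than stopping at the Early Termination Visit, so that recorded post-withdrawal events up to that point stay in.
2. Show onsets after Week 24 separately, with the patients actually followed as denominator. The Cohort 3 patients in it are self-selected, so it is descriptive only.
3. Footnote that rollovers have no Week 28 visit and that events with onset after extension entry are not counted in these tables.
4. Separately, footnote the Grade 3–4 laboratory summaries over all post-baseline visits that Week 28 adds an assessment rollovers do not have, or also give that figure through Week 24.

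The cost is a few extra tables and two TEAE windows that must be labelled clearly. No data are lost. The equal-window versions do not correct for differences in time to dropout, which the planned Kaplan-Meier curve of time to last dose will show.
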